RQ1: To what extent do parents taking part in BB4K's group sessions have improved self-efficacy measured by the Tool of Parental Self Efficacy (TOPSE) at five months post-randomisation compared to parents who do not receive the intervention? (Primary outcome, short- and medium-term)

As outlined in the ToC, we also expect to see changes in other important, but secondary outcomes, such as reduction in children experiencing behavioural issues at home or improved parent–child relationship and bonding.

The pilot evaluation will address the following secondary research questions:

RQ2: To what extent do children taking part in BB4K's group sessions have reduced behavioural issues at home measured by the Brief Assessment Checklist for Children at five months post-randomisation, compared to children who do not receive the intervention? (Secondary outcome, medium-term)

RQ3: To what extent do parents and children taking part in BB4K's group sessions have improved parent–child relationship and bonding measured by the closeness scale of the Child Parent Relationship Scale at five months post randomisation, compared to parents and children who do not receive the intervention? (Secondary outcome, medium-term)

RQ4: To what extent the BB4K's group sessions lead to improvements in all above areas at five months post randomisation for certain groups of parents and children (including: children in the following age bands: 3–5; 6–8; 9–11; children's gender and ethnicity) taking part in BB4K compared to the same groups of parent and children who do not receive the intervention? (Subgroup analysis)

Design

The impact evaluation of BB4K will be a cohort two-armed, randomised waitlist trial with 72 pairs of children (aged 3–11) and their non-perpetrating parents. The design allows for participants to be exposed to BB4K in cohorts (i.e. Cohort 1 and 2), allowing for staggered recruitment and delivery. Delivery will take place in cohorts for reasons of capacity and recruitment practicalities. In the waitlist design, all participants referred to BB4K will eventually take part in the intervention. Randomising the start date of implementation will allow participants with the later start date to act as a comparison group.

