Randomisation for Cohort 2 (scheduled for Sep 2024): Parents and children from Cohort 2 will be randomised to the treatment condition, i.e. to receive BB4K immediately in Sep 2024, or to the waitlist treatment condition, who will receive the intervention 5 months after the treatment groups, i.e. in March 2025. Up to 40 parent-child pairs will be recruited in Cohort 2 and this cohort will also include children aged 3–5. There will be up to 16 families with children aged 3–5, and up to 24 families with children aged 6–11. Half of the families with younger children (3–5) will be allocated to the treatment, and the remaining half to the waitlist treatment. Families with children aged 6–11 will be allocated to the treatment and waitlist treatment condition with 2:1 assignment, i.e. 16 parent-child pairs will be allocated to the treatment group, and 8 parent-child pairs will be allocated to the waitlist treatment group. Parent-child pairs will be stratified by region and on whether they are eligible for the younger or older group based on the child's age classification prior to randomisation. This will ensure balance across treatment and waitlist treatment arms across sites and younger/older groups after randomisation.

It is important to note that the transition period for the waitlist treatment group is long, particularly for the waitlist treatment in Cohort 1. The timeline was selected to accommodate PACT's capacity for delivery (maximum two or three groups) and to enable outcomes to emerge (i.e. the timeline is designed to allow two months between endline and follow-up data collection).

The differential waitlist times has the potential to introduce a number of biases that could impact the validity and reliability of the findings. Cohort 1 waitlist participants who have to wait three months longer (8 months compared to Cohort 2's 5 months) to receive the programme may be more likely to drop out of the study. Likewise, longer waiting times might affect participants' expectations or motivation regarding the programme. Additionally, those with a longer waitlist time may experience changes over time, like an improvement or worsening of outcomes, or may be more likely to seek additional support which could confound the effects of the programme.

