To limit the effect of these factors, anonymity and confidentiality are emphasised in communication with participants, and clear standardised instructions are provided. Likewise, feedback on the experience of using the surveys will be collected as part of the study and a review of selected outcome measures will occur between Cohort 1 and Cohort 2 (for details, see the following section).

Cohort 1 parent–child pairs will complete the baseline survey between April and May 2024, the endline between July and August 2024, and the follow-up between September and October 2024. Cohort 2 parent–child pairs will complete the baseline survey in September 2024, the endline between December 2024 and January 2025, and the follow-up survey between February and March 2025.

	Cohort 1		Cohort 2	
	Treatment (2 groups)	Waitlist treatment (2 groups)	Treatment (3 groups)	Waitlist treatment (2 groups)
Baseline survey	Apr–May 24	Apr–May 24	Sep 24	Sep 24
Delivery	May–Jul 24 (2 groups)	Jan–Mar 25 (2 groups)	Sep–Dec 24 (3 groups)	Mar–May 25 (2 groups)
Endline survey	Jul–Aug 24	Jul–Aug 24	Dec 24–Jan 25	Dec 24–Jan 25
Follow-up survey	Sep–Oct 24	Sep–Oct 24	Feb–Mar 25	Feb–Mar 25

Review of outcome measures before they are used with Cohort 2

It is important to note that measuring outcomes for children and young people who have experienced domestic abuse can be a challenging task. While the selected measures have been used with a general population, these are not validated specifically for this group. Therefore, we will review the suitability of using the secondary outcome measures with Cohort 1. As part of this, we will review the ease of administration of the self-report surveys, including take up and time needed for administration with Cohort 1. We will also assess whether the scores are normally distributed.

Following the review, a decision will be made on whether we will employ the same outcome measures with Cohort 2.

Analysis plan

The Statistical Analysis Guidance produced by What Works for Children’s Social Care is still applicable for the work of Foundations.¹⁷

Primary analysis

The pilot is designed as a cohort two-armed, randomised waitlist trial.

¹⁷ See <https://whatworks-csc.org.uk/wp-content/uploads/WWCSC-RCT-Statistical-Analysis-Guidance-V1.2.pdf>

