The primary outcome is the TOPSE score at follow-up,¹⁸ controlling for baseline TOPSE score. We will estimate the mean difference in TOPSE scores between participating families in BB4K and the waitlist treatment group participants. The primary analysis will use a mixed effects model allowing for different outcome variance between the treatment group and waitlist treatment group arms, and heteroscedastic individual-level errors. The model will control for delivery site, child age,¹⁹ and baseline TOPSE score via fixed effects. The between-cluster variation in the treatment group groups will be modelled as a random effect. The model is not powered to investigate differences in treatment effects between sites.

The analysis model will be:

$$Y_{ijk} = \beta_0 + \sum_{k=1}^3 \beta_k s_k + \gamma Y_{0ijk} + \delta X_{ijk} + \theta t_{ijk} + t_{ijk} u_{jk} + (1 - t_{ijk}) r_{ijk} + t_{ijk} \varepsilon_{ijk}$$

- Y_{ijk} is the outcome at follow up for parent i in treatment group j and sites k
- There are three sites $k= 1,2,3$
- There are $j=9$ clusters corresponding to 5 treatment group and 4 waitlist treatment groups
- Sites $k=1,2,3$
- β_k represents difference in outcomes between sites
- θ is the treatment effect.

In line with Foundation's Statistical Guidance, the analyses will follow an intention-to-treat (ITT) approach. The analysis will include all randomised children and parents in the groups to which they were randomly assigned, regardless of the treatment actually received, withdrawal from BB4K post-randomisation, or deviations in programme implementation. This principle is key in ensuring an unbiased analysis of intervention effects. The difference between the treatment and waitlist treatment groups at endline will be expressed as a standardised effect size using Hedges' g with 95% confidence intervals. The primary analysis will also include detailed descriptive analysis: histograms, means, quartiles, and standard deviations, for all measures, groups, and time points. All analysis will be scripted to allow for transparency and replication and will be uploaded to GitHub.

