Upon receipt from PACT, a researcher will conduct an initial check of the data received against our IPE MI plan and follow up with PACT to fill data gaps and clarify any discrepancies. After we are confident we have the correct data, our data services team processes the data (e.g. ensures consistent formatting; reorganises it for evaluation purpose) and creates an SPSS file and tables for descriptive analysis using a data specification the research team develops. The process is repeated at Wave 2 (the final analysis wave) and tables are created that show change between waves 1 and 2.

Triangulation

We will take a systematic approach to the analysis of all strands of data collection (impact and IPE) to generate insight that covers both the breadth of all participating families and the depth of experiences and impacts for different types of families (different Cohorts or younger/older age groups). To incorporate the information from all strands of data collection we will design an analysis framework. The framework will be structured around the research questions. It will be set up to allow us to identify differences across parents and children and stakeholder groups. We will organise an internal analysis workshop to triangulate the evidence gathered into a coherent set of findings; to explore possible convergence and divergence of trends and themes and anticipate their plausible outcomes; and draft recommendations for the programme.

Evaluation experiments

We will conduct two experiments to answer RQ4 of the implementation and process evaluation, focusing on strategies to boost response rates to the endline and follow-up surveys. The experiments will be conducted 5 months after randomisation. At this point, waitlist treatment groups have not yet taken part in BB4K. These experiments include:

1. Testing use of in-person events for survey completion
2. Testing use of £10 incentives on endline survey response.

Experiment 1: Testing use of in-person events for survey completion

Experiment 1 involves testing the use of in-person events on follow-up survey completion with Cohort 1 only. Cohort 1 has two treatment groups and two waitlist treatment groups (32 families total). One treatment group and one waitlist treatment group will take part in the celebration events (16 families) and the other treatment and waitlist treatment groups will not (16 families).

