Outcome measures are not optimal	Low/Medium	Outcome measures do not align with the theory, are difficult to administer, or measure a change that cannot be realised within the timeline.	Our experienced team will ensure that outcome measures are fit for purpose. This includes expert assessment and consultations with PACT to allow us to select the most robust instruments.

Timeline

Dates	Activity	Staff responsible/ Leading
January to April 2024	Onboarding and set-up (including evaluation protocol, ethics and data protection)	IFF Research
April to May 2024	Cohort 1 delivery set-up, randomisation and baseline survey (2 research/treatment groups and 2 non-research/waitlist treatment groups)	IFF Research/PACT
May to July 2024	Cohort 1 group delivery (2 groups of aged 6-11s) – 8 sessions over 10 weeks	PACT
July 2024	Cohort 1 endline survey	IFF Research
June to August 2024	Implementation and process evaluation Wave 1	IFF Research
September to October 2024	Cohort 1 follow-up survey	IFF Research
January to March 2025	Cohort 1 waitlist treatment group delivery	PACT
August to September 2024	Cohort 2 delivery set-up, randomisation and baseline survey (3 research/treatment groups and 2 non-research/waitlist treatment groups)	IFF Research/PACT
August 2024	Cost evaluation data collection Wave 1	IFF Research
September to December 2024	Cohort 2 group delivery (2 groups of aged 5–11s; 1 group age 3–5)	PACT

December 2024	Cohort 2 endline survey	IFF Research
November 2024	Mid-point grant progress report	IFF Research
December 2024 to January 2025	Implementation and process evaluation Wave 2	IFF Research
January to March 2025	Interim report	IFF Research
March 2025	Cohort 2 follow-up survey	IFF Research
April 2025	Cost evaluation data collection Wave 2	IFF Research
May to September 2025	Final reporting	IFF Research

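### Cohort 2's primary follow-up survey overlaps the start of waitlist delivery in March 2025, so up to 16 of the 32 controls could answer after some BB4K sessions

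*Protocol*

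**What the plan says.** Under Primary analysis, "The primary outcome is the TOPSE score at follow-up"; a footnote explains that follow-up was chosen over endline to give outcomes time to appear. RQ1 sets the comparison "at five months post-randomisation compared to parents who do not receive the intervention".

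For Cohort 2, the text under Data collection places "the follow-up survey between February and March 2025", and the table there gives the same two months for both arms. The Timeline has a row "Cohort 2 follow-up survey" dated March 2025 only.

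Under Randomisation, the Cohort 2 waitlist arm is the one "who will receive the intervention 5 months after the treatment groups, i.e. in March 2025". The Data collection table shows its delivery running from March to May 2025 in two groups.

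Follow-up surveys go out by email and are chased with reminders and telephone calls. The primary analysis is by intention to treat, whatever treatment a family received. The Randomisation section discusses bias from unequal waiting times in the two cohorts but not this overlap.

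**The concern.** March 2025 is one of the two follow-up months in Data collection, the only follow-up month in the Timeline, and the month in which Cohort 2 controls start the programme. A waitlist parent who returns TOPSE after a first session is no longer a parent who has not received the intervention, yet counts as one. Planned chasing makes late returns likely.

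If early sessions help, the control mean rises and the estimated effect moves toward zero. That matters in a pilot meant to judge evidence of promise. A later analysis can describe the exposure but cannot recover the unexposed score.

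**Working it through.** **1. Overlap, by cohort**

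| | Follow-up survey | Waitlist delivery | Shared month |
|---|---|---|---|
| Cohort 1 | Sep–Oct 2024 | Jan–Mar 2025 | none |
| Cohort 2 (Data collection) | Feb–Mar 2025 | Mar–May 2025 | March |
| Cohort 2 (Timeline) | Mar 2025 | not listed | March, from the delivery dates above |

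**2. Who could be affected (Randomisation)**

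- Treatment: 16 + (8 + 16) = 40. Waitlist: 16 + (8 + 8) = 32. Both match the stated arm sizes.
- Cohort 2 share of the waitlist arm: 16/32 = 50%.
- Cohort 1 takes only ages 6–11, so all 8 controls aged 3–5 are in Cohort 2.

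**3. How much exposure is possible**

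Sessions are weekly, with 8 for ages 6–11 and 12 for ages 3–5. March has 31 days, and 31/7 = 4.4, so at most about 4–5 sessions fit before the month ends.

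A late-March start would reduce this, but not easily for the 3–5 group. March to May 2025 holds 13 weeks beginning on a Monday (3 March to 26 May). Twelve weekly sessions must then start by about the week of 10 March, even with no school break.

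**4. Month arithmetic**

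- September 2024 + 5 months = February 2025. September to March is 6 calendar months.
- With month-level dates, the end of September to the start of March is about 5 months. The 5-month interval and the March start therefore agree only at that extreme.
- From randomisation in August–September (Randomisation table) to a March survey is about 5 to 7 months, against RQ1's five.
- Treatment delivery ending in December + 2 months = February, which matches the planned gap of roughly two months.

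**5. The plan's own figure**

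The stated MDES is 0.79 SD. The inputs are P = 40/72, J = 9 clusters of n = 8, ICC = 0.1 (the table value), r = 0.56 (R² = 0.3136), two-sided alpha 0.05 and power 0.80:

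MDES = (1.96 + 0.84) × √[0.1/(P(1−P)×9) + 0.9×(1−0.3136)/(P(1−P)×72)] = 0.791.

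This reproduces 0.79, with SE = 0.791/2.80 = 0.282. The text's ICC of 0.01 does not reproduce it under this formula; that is a separate matter.

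**6. Dilution**

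Let f be the share of the 16 who answer after starting, and g the share of the full effect they already have. Both are assumptions, as the protocol gives neither. Then:

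observed effect ≈ true effect × (1 − (16/32) × f × g), and power = Φ(observed/0.282 − 1.96).

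| f | g | Shrinkage | 0.79 SD becomes | Power |
|---|---|---|---|---|
| 0 | – | 0% | 0.79 | 79.9% |
| 1 | 0.10 | 5% | 0.75 | 75.7% |
| 0.5 | 0.25 | 6.25% | 0.74 | 74.6% |
| 1 | 0.25 | 12.5% | 0.69 | 68.7% |
| 1 | 0.50 | 25% | 0.59 | 55.5% |

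In the exploratory 3–5 subgroup the factor 0.5 drops out and shrinkage is f × g: 12.5% at f = 0.5, g = 0.25, and 25% at f = 1, g = 0.25.

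**The case against.** The best defence is that the overlap is possible rather than certain. Dates are given by month, February responders are unaffected, and even a first-week start gives only a few sessions. The protocol chose follow-up over endline because it expects outcomes to take time, which argues for a small g. The endline comparison (December–January) falls wholly before any waitlist delivery and uses the same model, so one uncontaminated contrast exists, though at an earlier time point. All of this stands, and it limits the size of the problem. It does not supply a rule that puts the survey before the first session.

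A reader might infer more than the document supports:

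- **That half the control arm will have been treated.** 16 of 32 is a ceiling and the exposure is partial.
- **That the protocol contradicts its own sentence** "At this point, waitlist treatment groups have not yet taken part in BB4K". That sentence belongs to the response-rate experiments. Experiment 1 concerns Cohort 1 in September 2024 and Experiment 2 concerns Cohort 2 in January 2025. Both precede waitlist delivery, so the sentence stays true.
- **That the home visit is itself early exposure.** The protocol places it within referral and triage, and nothing says it follows the wait.
- **That the exposure could not be detected.** Attendance at each session is recorded in the management information, so exposure can be dated if survey dates are also kept.
- **That late waitlist scores should be set to missing in the primary analysis.** This would be a post-randomisation exclusion in one arm only, contrary to the stated intention-to-treat rule.

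An analysis plan not shown here might handle late returns. The conflicting dates, however, are fixed in the protocol, and no analysis rule can undo exposure.

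**Conclusion.** The concern holds as a scheduling conflict at the primary time point. Cohort 2 follow-up and waitlist delivery share March 2025, with no sequencing rule in the protocol at hand. Up to 16 of 32 controls, including all 8 aged 3–5, could be partly exposed when TOPSE is measured.

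The direction, toward no effect, assumes that early sessions help. The size depends on f and g, which the protocol does not give; about 6% to 12.5% shrinkage is illustrative, not an estimate. The formula also weights all controls equally and ignores missing data. The overlap itself, the count of 16 and the differing survey dates in Data collection and the Timeline rest on the document alone.

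**What to change.** - Open the Cohort 2 follow-up survey in both arms at the start of February 2025 and close it in both arms before the first waitlist session. This fits RQ1's five months from September and the two-month gap after December. The point requires no change to delivery dates.
- Correct the Timeline row to match Data collection, and reconcile the 5-month interval with the March 2025 start under Randomisation.
- Record each family's survey completion date and first-session date.
- Keep all randomised families in the intention-to-treat primary analysis. Add a sensitivity analysis that flags or excludes waitlist TOPSE scores dated after the first session.

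The cost is a Cohort 2 chasing window of about one month instead of two. That is a real cost, because the Risks section rates low response to outcome assessment as medium/high; early reminders and calls in February would have to carry the load. The rest is a date correction, two recorded dates and one sensitivity analysis.

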There is only one treatment condition: i.e. children and their non-abusive parent will receive BB4K sessions. In total 40 parent–child pairs referred to BB4K will be assigned to the treatment group. Parents and children recruited in Cohort 1 and assigned to the treatment condition (i.e. 16 parent–child pairs) will receive BB4K sessions between May and July 2024, while those recruited in Cohort 2 and assigned to the treatment arm (i.e. 24 pairs) will receive BB4K sessions between September and December 2024.

A total of 32 parent–child pairs will be assigned to the waitlist treatment. They will be given access to the new digital platform, ‘Bounce’, in addition to the business as usual support they are receiving from other services, before they receive the BB4K support (see ‘Business as usual’ for more information on the additional support offered). For this evaluation, that means that we are assessing the effect of the group sessions rather than the full package of support offered as part of BB4K which includes ‘Bounce’ (but is not required for all BB4K families to use). This has the benefits of offering a support to the waitlist group and may improve retention in the waitlist treatment group.

Given that the delivery of BB4K will take place sequentially in two cohorts, randomisation will occur at two different time points (see ‘Randomisation’ for more information).

[figure not shown]
Trial type and number of arms		Two-arm, cohort, randomised waitlist trial
Unit of randomisation		Parent–child pairs (family level)
Block (stratification) variables		Delivery site (age ⁷)
Primary outcome	variable	Parents’ self-efficacy
	measure (instrument, scale)	Tool of Parental Self Efficacy (A multi-dimensional parent self-report of 48 statements within 8 scales measuring parental self-efficacy. The score ranges between 0 and 60.)
	variable(s)	
 1. Children’s behavioural issues at home 2. Parent–child relationship and bonding

⁷ Relevant for Cohort 2 only, as only children between 6 and 11 will take part in Cohort 1.

Secondary outcome(s)	measure(s) (instrument, scale)	
1. Brief Assessment Checklist for Children (20 items parent self-report screening and monitoring scale. The total score is between 0 and 40)2. Child Parent Relationship Scale – closeness scale (Parent self-report, 10 items, ranging between 10 and 50)
-----------------------------	---	---

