The diagram below shows the participants' journey through the trial.

Randomisation

As BB4K is a group-based programme, randomisation will be executed in blocks according to children's age and stratified by site. Allocation into treatment or waitlist control will be done at the parent-child level. Randomisation of children-parent pairs will be undertaken after families have been referred to BB4K and informed consent has been provided. Randomised blocks will be used at each delivery site to allocate participants to either treatment or waitlist treatment groups.

Randomisation will occur at two different time points for Cohort 1 and 2, as follows:

Randomisation for Cohort 1 (scheduled for Apr 2024): Once parents and children in Cohort 1 are recruited they will be randomised to either receive BB4K immediately, i.e. between May and July 2024, or to be allocated to the waitlist treatment group who will receive BB4K 8 months after the treatment group, i.e. in January 2025. In total, 32 parent-child pairs will be randomised to two treatment and two waitlist treatment groups. Given that group delivery is organised regionally, with key covariates likely to vary across delivery sites, stratifying by delivery site ensures the treatment and waitlist treatment are balanced across sites. Groups will be blocked on the age of the children with age bandings: 6–8, and 9–11.

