If there is less than 5% missingness overall, we will undertake a complete case analysis as the primary analysis. However, it can be problematic to apply the intention-to-treat principle if parents are not able to complete the outcome surveys. To deal with missing data we will complete the following analyses. First, we will report on attrition from analysis and attrition from BB4K including reasons. Second, we will explore the extent of missingness, and then we will assess the pattern of missingness. To assess whether there were systematic differences between those who did not complete the outcome surveys and those who did, we will model missingness through a logistic

¹⁸ The follow-up measure is used instead of the endline measure to allow for ample time for outcomes to materialise.

¹⁹ As we stratify (block) by region and age.

regression model at follow-up as a function of key covariates, including treatment, age of child, and region to assess if any covariates are associated with missing data.

For each outcome measure, we will address any item non-response by using a mean of the completed items.

If values on covariates are missing and the overall percentage of the missing covariate is over 5% and smaller than 40%, we will use multiple imputation of missing covariates.

Secondary analysis

To assess impact for the secondary outcomes (i.e. child behaviour and parent–child relationship bonding) we will employ the same principles as the primary outcome analysis.

Early impact analysis using the endline survey

To explore the timing of when outcomes can be expected to materialise, and to capitalise on existing contact with treatment group participants still being in regular contact with the programme (assuming this will support treatment group response rates as low response rate to the surveys is a key risk to the evaluation), an endline survey will be deployed once the treatment groups complete the BB4K programme.

Those in the treatment group will complete the endline survey at the end of the final BB4K session. The waitlist treatment group will be sent the endline survey to complete via email.

Early impacts will be assessed using the same analysis strategy outlined for the primary outcome analysis.

Subgroup analysis

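### The primary model omits cohort, although families are randomised separately by cohort at different ratios, so about 13% of any cohort difference left after baseline adjustment enters the treatment effect

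*Protocol*

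**What the plan says.** The Design section of the protocol explains that "randomisation will occur at two different time points", once for each cohort. The Randomisation section and its summary table then set the ratios.

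- Cohort 1: "In total, 32 parent-child pairs will be randomised to two treatment and two waitlist treatment groups", which is 16:16. The note on the blocking variable in the Design section adds that "only children between 6 and 11 will take part in Cohort 1".
- Cohort 2, ages 3–5 (up to 16 families): "Half of the families with younger children (3–5) will be allocated to the treatment, and the remaining half to the waitlist treatment", which is 8:8.
- Cohort 2, ages 6–11 (up to 24 families): these "will be allocated to the treatment and waitlist treatment condition with 2:1 assignment", which is 16:8.

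Under Analysis plan, Primary analysis, the outcome is follow-up TOPSE: "The model will control for delivery site, child age" and baseline TOPSE as fixed effects, with a random effect for treatment groups. The printed equation has site terms, the baseline score and one further covariate term. Footnote 19 gives the reason for the covariates: "As we stratify (block) by region and age". Neither the text nor the footnote names cohort. The secondary and endline analyses are to follow the same approach.

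**The concern.** The authors clearly mean to adjust for the factors used in the randomisation, but the list leaves out the one across which the ratio changes. Where the chance of treatment differs between strata and the stratum is not in the model, the arms differ in stratum mix by expectation and not only by chance. The Randomisation section attributes any baseline imbalance to chance; for cohort membership that is not so.

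Anything that moves follow-up TOPSE between cohorts, such as season or a change in case-mix not captured at baseline, is then partly counted as treatment effect. The direction cannot be known in advance. The estimate affected is the one used to judge evidence of promise and the viability of a full trial. Because the protocol fixes the covariate list, this is not a detail left open for a later analysis plan.

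**Working it through.** **Inputs.** Planned counts are from the Randomisation section. The baseline correlation of 0.56, the 40:32 split, nine groups of eight and the MDES of 0.79 are from the sample size section.

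| Stratum | Treatment | Waitlist | Chance of treatment |
|---|---|---|---|
| Cohort 1, 6–11 | 16 | 16 | 50% |
| Cohort 2, 3–5 | 8 | 8 | 50% |
| Cohort 2, 6–11 | 16 | 8 | 67% |

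**The plan's own figure.** With P(1−P) = (40/72)(32/72) = 0.247, a group ICC of 0.1 (the table's value) and R² = 0.56² = 0.3136 at the individual level:

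SE = √[0.1/(0.247 × 9) + 0.9 × 0.6864/(0.247 × 72)] = √(0.0450 + 0.0347) = 0.282

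MDES = (1.960 + 0.842) × 0.282 = 0.79

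This reproduces the stated value, though not uniquely. The same formula with the ICC of 0.01 given in the text yields 0.58, and other variants with 0.01 also reach 0.79. In all cases the stated MDES corresponds to an SE of about 0.79/2.80 = 0.28.

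**Imbalance in cohort.** The Cohort 2 share overall is 24/40 = 60% of treatment and 16/32 = 50% of waitlist. Among ages 6–11 it is 16/32 = 50% against 8/24 = 33%, a gap of 0.167. Among ages 3–5 all pairs are in Cohort 2, so the gap is 0.

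**Fraction that leaks.** The omitted-variable result says that the bias equals the cohort difference times the treatment coefficient from regressing cohort on treatment and the included covariates.

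- No age term: 0.60 − 0.50 = 0.100.
- Age as younger/older: each age stratum gets weight n₁n₀/(n₁+n₀). Ages 6–11 get 32 × 24/56 = 13.71; ages 3–5 get 8 × 8/16 = 4. Leakage = 0.167 × 13.71/17.71 = 0.129.
- Three age bands (Cohort 2 ages 6–11 assumed split evenly): 0.129. Linear age (assumed ages 4, 7 and 10): 0.119.
- Allowing for the treatment-group random effect with ICC 0.01 to 0.1: 0.129 to 0.130 with categorical age.

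The planned age adjustment therefore does not remove the leak; it raises it slightly.

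**Size.** The documents give no cohort difference. The range below is an assumption and is conditional on baseline TOPSE. The unclustered SE is √(0.6864/17.71) = 0.197.

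| Assumed cohort difference (SD) | Bias (SD) | Bias / 0.197 | Bias / 0.282 | Share of 0.79 |
|---|---|---|---|---|
| 0.2 | 0.026 | 0.13 | 0.09 | 3% |
| 0.5 | 0.065 | 0.33 | 0.23 | 8% |
| 0.8 | 0.103 | 0.52 | 0.37 | 13% |

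Without clustering, the two-sided type I error would be about 5.2%, 6.2% and 8.2% in the three rows.

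**Cost of adding cohort.** Summing n₁n₀/(n₁+n₀) over the three strata gives 8 + 4 + 5.33 = 17.33 in place of 17.71. The SE ratio is √(17.71/17.33) = 1.011, and the leakage becomes 0.

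**The case against.** The best case against the point is that the bias is small and may be smaller than the headline fraction suggests. Most of that case stands.

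- *Baseline TOPSE is in the model.* Only the difference left after baseline adjustment leaks. If a raw difference of 0.3 to 0.8 SD were equally present at baseline, with 0.56 as the slope, 0.44 of it would remain (0.13 to 0.35 SD). The bias would then be 0.017 to 0.045 SD.
- *Site is in the model.* Suppose the new site recruits only in Cohort 2, with an equal share in each Cohort 2 cell. Adding an indicator for that site to the regression on treatment and age bands lowers the fraction from 0.129 to about 0.11, 0.10 or 0.08 when the site holds 33%, 50% or 67% of Cohort 2. Site-by-cohort counts are not given, so this cannot be settled.
- *Several visible cohort differences hardly touch the primary outcome.* A reader might infer that the response experiments or the 8- against 5-month waits drive the bias. The documents do not support that. The Cohort 1 events cover one treatment and one waitlist group. The Cohort 2 incentive concerns the endline survey, whereas the primary outcome is at follow-up. Both cohorts are followed up about five months after randomisation, before waitlist delivery is scheduled to start; only anticipation of a longer wait could act earlier. Season and residual case-mix remain as plausible sources.
- *The protocol hedges.* The Randomisation section discusses bias from the differing waits and says adjustment for confounders will be considered if needed. It names neither cohort nor a trigger, so it does not replace a prespecified term.

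None of this removes the mismatch between the randomisation and the model.

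**Conclusion.** The point holds as a modest, systematic bias and is graded should-fix. About 0.129 of the cohort difference remaining after baseline adjustment enters the treatment effect, before the site term. For an assumed 0.2 to 0.8 SD, that is 0.03 to 0.10 SD, or roughly a tenth to a half of a standard error, depending on whether clustering is counted.

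A reader might infer that a cohort difference passes in full into the result, or that the primary comparison is invalid. Neither follows: about 87% of the difference does not leak, and a cohort difference of about 0.78 SD after baseline adjustment (0.1/0.129) is needed for a bias of 0.1 SD. The conclusion rests on the planned counts being met, on the assumed range for the cohort difference, and on a site pattern that does not itself separate the cohorts.

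**What to change.** Add a fixed effect for cohort to the primary model, keeping site, child age and baseline TOPSE. With age coded as younger/older this is the same as fitting the cohort-by-age randomisation stratum. Cohort should be added alongside child age, not in place of it. Extend footnote 19 so that it names cohort among the randomisation factors, and state that the secondary and endline analyses use the same model. Make the change before outcomes are examined by arm, so that the term cannot look data-driven. The cost is a line in the analysis section, one degree of freedom and about 1% in standard error; no new data are needed.
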